15.2 CTCAE V 4.0

15.3 RTOG COSMESIS SCALES

1. STUDY DESIGN/SUMMARY

1.1 SUMMARY: This is a single arm phase II study design, evaluating the pathologic response (primary endpoint) as well as toxicity, cosmetic outcome, quality of life, and oncologic outcomes (secondary endpoints) to pre-operative stereotactic body radiotherapy (SBRT) to intact breast tumors in patients with hormone-receptor positive early stage breast cancer.

1.2 SCHEMA

2. OBJECTIVES

2.1 PRIMARY OBJECTIVE: To determine the rate of Residual Cancer Burden (RCB) designation 0 (also known as pathologic complete response (pCR)) and RCB I designation (combined endpoint of either of those designations) 7-14 days after pre-operative SBRT to intact breast tumors.

2.2 SECONDARY OBJECTIVES

2.2.1 To determine the rate of severe acute toxicity, defined as any CTCAE v4 grade 3 or higher toxicity noted from RT delivery up to 90 days after completion of surgery.

2.2.2 To determine the rate of poor cosmetic outcomes from both provider and patient perspectives up to 3 years after pre-operative SBRT to intact breast tumors using the RTOG (Radiation therapy oncology group) cosmesis scale and digital images.

2.2.3 To measure local recurrence rate

2.2.4 To assess patient reported satisfaction and quality of life with treatment using the Breast Cancer Treatment Outcomes Scale (BCTOS)

3. BACKGROUND

3.1 INVESTIGATIONAL AGENTS: none

3.2 STUDY DISEASE: Early stage clinically node-negative hormone receptor positive breast cancer

3.3 RATIONALE:

Standard treatment for early stage breast cancers includes a 3-6.5 week course of whole breast radiation following breast conservative surgery. Studies have demonstrated that the requirement for multiple consecutive weeks of adjuvant radiation treatment puts older women, those who live in low-income areas, and those who live far from radiation centers at a disadvantage, leading to omission of this key part of definitive therapy.^{1,2} At the same time, it has been observed that patients with certain low-risk features such as small ($\leq 2\text{cm}$) estrogen receptor (ER) positive tumors and negative lymph nodes have lower rates of local recurrence, and tend most commonly to recur in the lumpectomy bed as opposed to elsewhere in the breast.³

These observations have led to the development of abbreviated radiation treatment regimens focused solely on the tumor bed, rather than the whole breast, an approach known as accelerated partial breast irradiation (APBI). This approach was developed in the 1990's and over time various techniques for the delivery of APBI have been developed, including interstitial catheter-based brachytherapy, balloon-based brachytherapy, and

October 10, 2023

Principal Investigator: [name]

IRB IRB00128074

APBI delivered using standard external beam radiotherapy with multiple non co-planar beam angles. Despite variability in technique, all these approaches are most commonly delivered in 10 treatment sessions delivered twice daily over 5 days; each treatment session delivers a higher dose of radiation as compared to conventional techniques with the goal of achieving a biologically equivalent dose to the tumor bed in fewer sessions.

Single-institution and registry data compiled since the inception of the APBI approach have demonstrated low rates of locoregional recurrence in appropriately selected patients and the early favorable experience with APBI led to a randomized trial, NSABP B-39/RTOG 0413 , which compared outcomes with the various techniques for APBI with the standard approach of whole breast irradiation.^{4,5} This study accrued over 4000 patients, and closed in 2013. Locoregional outcomes have not yet been published, and at this time there is no published phase III data demonstrating the equivalence of APBI and standard whole breast RT. However, in light of the weight of evidence accumulated from decades of retrospective data on the approach of APBI, consensus guidelines for the appropriate use of APBI outside the setting of a clinical trial were developed in 2009, and the ASTRO update was recently published in late 2016.⁶ In summary of these guidelines, APBI has been found to be an acceptable technique for patients with early stage, node-negative breast cancer with low-risk features, and we await randomized data to determine if the approach can be expanded to patients with higher-risk features.

Thus, at this time, there is considerable data to support the use of APBI in well-selected low risk patients, but the optimal technique for delivery of APBI has not been determined. The ideal technique would combine accessibility (delivered using widely available technology, with low expense, and using the lowest number of treatment fractions) with excellent cosmetic results (recalling that the movement for breast conservation emerged from the desire to provide equivalent oncologic outcomes compared to mastectomy with superior cosmetic results).

The most accessible technique for APBI is external beam radiation, as this can be delivered via a standard linear accelerator and does not require extensive technical training. On the NSABP B-39 study, which allowed any of the three common techniques for APBI, 75% of patients were treated with EBRT. However, this technique has been associated with poorer cosmesis and higher rates of soft tissue fibrosis compared to whole breast radiation.^{7,8} We await formal publication of the cosmetic outcomes using EBRT from NSABP B-39, but at this time there is ongoing concern that this approach results in inferior cosmesis compared to whole breast RT due to asymmetric fibrosis of the breast in the treated area. In addition, this approach still requires 10 treatment sessions delivered twice daily, 6 hours apart, a schedule that is cumbersome for many women.

Single-fraction approaches offer a more convenient schedule, and have been explored most commonly in the setting of intra-operative treatment. There are several techniques

for this approach.^{9,10} The most widely marketed IORT approach in the US has been the Targit technique, using a KV source to deliver radiation intra-operatively in a setting that does not require special shielding. However, a phase III study comparing this approach to whole breast external beam radiation demonstrated higher local recurrence risk with the Targit technique compared to whole breast RT.⁹ This finding may relate to the very low radiation dose that reaches a depth of 1 cm deep to the surface of the tumor bed, a depth generally considered to be within the clinical target volume for breast cancer. While 20 Gy is prescribed to the cavity surface, a sub-therapeutic dose of 7 Gy penetrates to a depth of 1 cm, a minimum depth presumed to be at risk for microscopic disease. Similar findings were reported using the ELIOT electron-based IORT technique, with a higher risk of local recurrence using IORT as compared to whole breast RT.¹⁰ In addition, the technology needed to deliver IORT using Targit and ELIOT techniques is costly and this not widely available in the US.

Thus, none of the currently popular approaches to APBI is ideal, either due to inferior efficacy, poorer cosmesis, high cost/need for specialized equipment, and/or inconvenience.

An alternative to the above strategies that mitigates many of these limitations is pre-operative single fraction SBRT. There are several potential advantages to this approach over a post- or intraoperative approach. First, it can be delivered with standard radiation equipment using linear accelerator technology that is available in the majority of radiation oncology departments in the US. Second, by treating an intact tumor and using MRI fusion for target delineation, the radiation target is well-defined compared to a postoperative bed that can be difficult to identify. Third, because the tumor is intact, the treatment area is smaller than a typical postoperative bed, decreasing radiation exposure to normal tissue, and the majority of the targeted volume is subsequently resected. Fourth, by treating pre-operatively, we overcome the theoretical concern of postoperative hypoxia in the tumor bed. Finally, a preoperative approach allows for real-time study of radiation response.

Investigators at Duke University have piloted this approach with excellent results: in a cohort of 32 patients, a maximum tolerated dose of 21 Gy has been determined, no grade 3 or 4 toxicities were seen, fibrosis at 18 months followup was minimal (58% grade 1, 10% grade 2, 3% grade 3) and cosmesis was rated as excellent or good in all patients.¹¹ While these phase I results are promising, the study cohort is very small. These findings warrant replication in a Phase II study such as the one we propose here.

Authors in the Netherlands recently published their preliminary results of preoperative accelerated partial breast irradiation using a hypofractionated approach of 40 Gy in 10 fractions delivered once daily over 2 weeks. Eligible patients include those aged > 60 years, cT1-2, pN0 and invasive ductal histology. Median follow-up for 70 patients was 23

October 10, 2023

Principal Investigator: [name]

IRB IRB00128074

months, and two ipsilateral breast tumor recurrences were diagnosed. In terms of patient reported outcomes, at 3 years 79% of patients were satisfied to very satisfied with their cosmetic result. After 36 months, only 11 (19%) patients were noted to have any fibrosis, and all cases were mild. In summary, the authors concluded that given the good to excellent cosmetic results and low complication and fibrosis rates, pre-operative APBI is a feasible technique for low-risk breast cancer patients.¹² This approach to ABPI has the disadvantage of a longer course of therapy as compared to SBRT. Pathologic response was not reported in this series.

Pathologic response to chemotherapy has been shown to be prognostic for both locoregional and survival outcomes in breast cancer, and has become an increasingly utilized endpoint in preoperative chemotherapy studies. Studies have demonstrated that lower-risk tumors such as those with ER positive/HER2 negative phenotype are less chemosensitive and thus less likely to show a pathologic complete response to chemotherapy.¹³ At the same time, response to chemotherapy is less prognostic in this setting.¹⁴ A more nuanced system of evaluating response in those tumors that do not show a pCR is the residual cancer burden (RCB) scoring system (REF), which evaluates tumor size, nodal involvement and cellularity has been demonstrated to be predictive of outcome and is used to define categories of less than complete response.¹⁵

While response to pre-operative chemotherapy is less prognostic in ER-positive disease, the opposite may be true in terms of radiation response. There is little data evaluating response to radiation to intact breast tumors, but data looking at the benefit of adjuvant radiation in breast cancer shows a greater impact of RT in reduction of locoregional recurrence, and a greater survival impact in ER positive tumors as compared to ER negative or triple negative.^{13,15} Thus, a better understanding of tumor response to radiation is critical. Unlike chemotherapy response, response to radiation may in fact be prognostic based on adjuvant RT data, and can be used as a baseline for future study.

Additionally, we also plan to study pathologic specimens for change in hormone receptor status, conversion of Ki 67, and presence of residual DCIS and evaluate the utility of these as biomarkers to predict response.

4. PATIENT SELECTION

4.1 INCLUSION CRITERIA

4.1.1 Female sex

4.1.2 Age \geq 50

4.1.3 Invasive ductal carcinoma

4.1.4 Clinically and radiographically T1 tumor

4.1.5 Clinically node negative

- 4.1.6 Clearly demarcated tumor on magnetic resonance imaging (MRI), as determined by treating physician (MRI may be done after enrollment if not done prior)
- 4.1.7 Planning breast conserving surgery
- 4.1.8 ≥10% expression of ER and/or PR
- 4.1.9 HER2- using the current College of American Pathologists guidelines
- 4.1.10 Post-menopausal
- 4.1.11 Willing and able to provide informed consent
- 4.1.12 Patient's case has been reviewed and approved for trial by medical oncologist

4.2 EXCLUSION CRITERIA

- 4.2.1 Medical conditions that may increase risk for poor cosmetic outcome (i.e. Lupus, rheumatoid arthritis, scleroderma)
- 4.2.2 Pure DCIS without invasive cancer
- 4.2.3 Patients who have received or will be receiving neoadjuvant systemic therapy, endocrine therapy, or targeted agents
- 4.2.4 Breast implant in the involved breast unless the implant will be removed prior to initiation of study treatment
- 4.2.5 Subjects without placement of a biopsy clip at the diagnostic procedure who are unwilling to undergo clip placement.
- 4.2.6 Unable to meet dosimetric constraints due to tumor location and/or patient anatomy
- 4.2.7 Planning mastectomy
- 4.2.8 Unable to tolerate prone positioning

4.3 INCLUSION OF WOMEN AND MINORITIES

Individuals of all races and ethnic groups are eligible for this trial. This trial is open to the accrual of post-menopausal women only.

5. REGISTRATION PROCEDURES

5.1 RECRUITMENT

Patients will be identified by screening in the surgical clinics. Patients will be referred to radiation oncology pre-operatively after screen identification. Once a subject has successfully completed all of the screening procedures and is considered eligible by the principal investigator, the subject can be enrolled in the study.

5.2 INFORMED CONSENT

All subjects considered for enrollment in the study must complete an IRB approved

October 10, 2023

Principal Investigator: [name]

IRB IRB00128074

informed consent prior to any study-specific procedures being performed. The investigator (or his/her designee) will explain to each subject the nature of the study, its purpose, the procedures involved, the expected duration, the potential risks and benefits involved and any discomfort it may entail. Each subject will be informed that participation in the study is voluntary, that she may withdraw from the study at any time, and that withdrawal of consent will not affect her subsequent medical treatment or relationship with the treating physician(s) or institution. The informed consent will be given by means of a standard written statement, written in non-technical language, which will be IRB approved. The subject should read and consider the statement before signing and dating it, and will be given a copy of the document. No subject will enter the study or have study-specific procedures performed before her informed consent has been obtained.

In accordance with the Health Information Portability and Accountability Act (HIPAA), the written informed consent document (or a separate document to be given in conjunction with the consent document) will include a subject authorization to release medical information to the study sponsor and supporting agencies and/or allow these bodies, a regulatory authority, or Institutional Review Board access to subjects' medical information that includes all hospital records relevant to the study, including subjects' medical history.

5.3 SCREENING/BASELINE ASSESSMENT AND PROCEDURES

Patients must undergo complete history and physical exam including complete clinical breast and regional nodal exam, weight, and Karnofsky performance status assessment within 30 days prior to enrollment. Patients must also have a biopsy confirmed invasive ductal breast cancer on which ER, PR, and Her2 receptor status must be assessed per CAP guidelines, as well as Ki67 documented. If possible, percent tumor cellularity should be reported on the biopsy specimen. Bilateral mammograms must have been performed within 120 days of study entry for all patients with an intact contralateral breast. A medical oncologist will also review the case prior to enrollment and determine need for formal consultation pre-operatively, specifically to ensure that adequate information is available based on the available tissue to inform treatment decisions in the event of pCR. MRI is not required to be done before enrollment but if an MRI was already done, this can be used for study purposes. The MRI must have been completed within 60 days of enrollment.

6. TREATMENT PLAN

6.1. FIDUCIAL PLACEMENT

October 10, 2023

Principal Investigator: [name]

IRB IRB00128074

Prior to treatment patients must have at least one radio-opaque fiducial marker placed in the tumor, which will be used for image guidance for precise radiation delivery. If a clip or clips have been placed at biopsy, they may serve as fiducial markers. The markers must be located within the tumor on the treatment planning MRI.

6.2 SIMULATION

All patients will undergo standard CT simulation with 2 mm cuts in the prone position with arms overhead and treated breast pendant, per our institutional procedure for prone breast simulation; if the treating physician deems appropriate, supine positioning is allowed. If MRI simulation is available in the clinical location, MRI simulation may be performed. Any palpable tumor will be marked with a BB. A Vac-fix bag will be required to standardize immobilization. Verification of fiducial marker placement and visibility will be confirmed at the time of simulation.

6.3 MRI FUSION

All patients will undergo MRI for target delineation. If patients have had diagnostic MRI within 60 days of study enrollment, this will be fused in our planning system to the CT simulation scan. This diagnostic MRI must have been performed in a dedicated breast surface coil with arms overhead. If the patient has not had such an MRI prior to enrollment, they will undergo MRI simulation in a breast surface coil. The following sequences will be fused to the CT scan for gross tumor delineation: axial T1, axial T2 with fat saturation, diffusion weighted imaging, and any additional sequences on which the tumor is clearly delineated as determined by the physician contouring.

6.4 RADIATION TREATMENT PLANNING

6.4.1 Target Volumes: The gross tumor volume (GTV) will be contoured using the fused MR images as well as the fiducial clip and any abnormality noted on CT. A uniform 1.5 cm expansion will be applied around the GTV to create the clinical target volume (CTV). The first 5mm of tissue deep to the patient's body surface and any chest wall (pectoralis muscle and deeper) if >1cm from the GTV will be excluded from this CTV volume. The exclusion of tissue under body surface relates to concerns for inaccurate dosimetry in the build-up region; this is standard in cooperative group breast protocols. The exclusion of chest wall from the target volume relates to the anatomic boundary created by this structure. To account for set-up uncertainty at the machine, we will generate two planning target volumes for generation of beam apertures: a GTV_21_PTV which is a 0.5 cm expansion of the GTV, and a CTV_15_PTV which is a 0.5 cm expansion of the CTV. Beam apertures may be smaller than 5 mm if dose constraints below can be met with smaller margins.

October 10, 2023

Principal Investigator: [name]

IRB IRB00128074

6.4.2 Organs at risk to be contoured will include: skin, each lung, each breast, spinal cord, heart, esophagus, thyroid and brachial plexus.

6.4.3 Treatment planning will be completed by a dosimetrist and may utilize arc therapy, multiple conformal beams, or intensity-modulated therapy, or a combination of these techniques. Dose will be normalized to provide a desired coverage to the GTV and CTV, detailed below. There is no restriction on photon energy, but electrons are prohibited. Patients will receive a single fraction of 21 Gy delivered to the GTV and 15 Gy to the CTV using a dose-painting method.

6.4.4 Target Localization and Treatment Delivery: All institutional protocols for stereotactic body radiotherapy pre-treatment quality assurance will be followed. At the time of treatment, patients will be positioned and immobilized as they were at the time of CT simulation, per institutional procedures. After set-up, cone beam CT (CBCT) will be used for localization as described in the section on target localization, unless CBCT is not technically feasible in a given patient. In addition to CBCT, kilovoltage on-board imaging (OBI) may also be used at the treating physician's discretion. Both biopsy clips and soft tissue will be used for registration. These images will be approved by the treating radiation oncologist before treatment proceeds.

6.4.5 Dose Constraints: Dose constraints are derived from the phase I experience with pre-operative SBRT at Duke University, establishing the safety of 21 Gy in a single fraction observing the following constraints:

6.4.5.1 Target volumes. All beam apertures will be demarcated by the PTVs to account for setup uncertainty. Beam apertures may be smaller than 5 mm if dose constraints below can be met with smaller margins. The GTV and CTV will be utilized for target dose-volume analysis. Subjects will receive a single fraction of 21Gy to the GTV, and 15 Gy to the CTV. The prescribed doses will cover >95% of the GTV and CTV respectively without exceeding maximum dose of 110% of the maximum prescribed dose.

6.4.5.2 Normal breast: <30% of the whole breast volume should receive 50% or more of the prescribed dose and <15% of the whole breast volume should receive the prescribed dose. This constraint is in line with the majority of partial breast irradiation protocols and will select for a group of patients with larger breasts. Irradiation to a larger relative volume of the breast may be associated with poorer cosmetic outcomes.

6.4.5.3 Contralateral breast: the contralateral whole breast volume should receive <10% of the prescribed dose to any point

6.4.5.4 Lungs:

1 Mean lung dose <3.6Gy

- 2 <37% of lung volume should receive 8Gy
- 3 <1500cc to 7Gy
- 4 <1000cc 7.6Gy

6.4.5.5 Heart: 1) Mean should not exceed 1.5Gy; 2) Point dose <5Gy.

6.4.5.6 Chest wall: D20cc <16.3Gy.

6.4.5.7 Thyroid: maximum point dose <10% of the prescribed dose

6.4.5.8 Brachial plexus: no point in the brachial plexus should receive more than 10% (2.1Gy maximum) of the maximum prescribed dose. The brachial plexus will be contoured as per RTOG consensus.

6.4.5.9 Skin dose: 1) Maximum dose will not exceed prescription dose. 2) Dose to 1cc: <15Gy dose to 10cc <8Gy. Of note the skin contour will consist of a 2 mm rind around the patient's body surface. The skin contour should extend to a level at least 10 cm above and 10 cm below the CTV-PTV structure.

6.4.5.10 Cord: maximum dose to 1 cc should be 1 Gy.

6.5 SURGERY

Resection of the tumor will be completed 7-14 days after delivery of radiation. Surgery will include sentinel node assessment per our institutional standards, but omission of sentinel biopsy is permitted in patients age 70 and over with no clinical evidence of nodal involvement. Resection of the tumor must include a 2mm margin of normal tissue. A re-excision vs post-operative whole breast RT should be considered if the margin is less. Positive margins must be re-excised unless deemed technically not feasible by the surgeon (eg anterior margin dissected to skin).

6.6 PATHOLOGIC ASSESSMENT:

Standard pathologic assessment per our institutional guidelines will be followed and additionally will include RCB analysis and repeat evaluation of Ki67 and receptor status (ER, PR and HER2) if there is any residual invasive cancer.

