9. CRITERIA FOR EVALUATION AND ENDPOINT DEFINITIONS

9.1 PATHOLOGIC RESPONSE – Standard pathologic assessment per our institutional guidelines will be followed. Additionally, we will include calculation of percent cellularity on the biopsy specimen, residual cancer burden (RCB) analysis and repeat evaluation of Ki67 and receptor status (ER, PR and Her2) if there is any residual invasive cancer at surgery. Residual cancer burden will be assessed by staff pathologists and is calculated using a published continuous index that combines pathologic measurements of the primary tumor (size and cellularity) and nodal metastases (number and size) (reference Symanns). This RCB index has been validated as a predictor of distant relapse.

9.2 ACUTE TOXICITY- Acute toxicity will be graded with the Common Terminology Criteria for Adverse Events (CTCAE) version 4. Grade ≥ 3 acute toxicity will be considered severe (Appendix 15.2).

9.3 COSMESIS- As noted in the introduction, early cosmetic results from other published pre-operative radiation series for early stage breast cancer have been favorable.¹¹ We expect similar favorable outcomes, and for the pre-operative single fraction cosmetic results to be equivalent to that of partial breast radiation results. We expect cosmesis to stabilize at 3 years following treatment and thus our endpoint will be to measure results at this timepoint. We will also assess cosmesis at specified time points per the study calendar to quantify changes in breast cosmesis over time.

Cosmetic results will be evaluated by both the patient and the physician. Patients will rate cosmesis using the Breast Cancer Treatment Outcome Scale (BCTOS), which will also be used to evaluate patient reported quality of life (Appendix 15.1). This self-report instrument has been used in a number of studies for this purpose and has both reliability and validity (reference Stanton AL, Krishnan L, Collins CA. Form or function? Part 1. Subjective cosmetic and functional correlates of quality of life in women treated with breast-conserving surgical procedures and radiotherapy. *Cancer* 91:2273-2281, 2001)

October 10, 2023

Principal Investigator: [name]

IRB IRB00128074

Patients will first complete this after informed consent, and then at multiple intervening assessment points up to 3-years of follow-up (see Study Calendar). At the same time points, patients will also score cosmesis using the RTOG 4-point scale.

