13. STATISTICAL CONSIDERATIONS

This is a prospective, single-arm study to determine the pathologic outcomes, acute toxicities, cosmetic outcomes, and local recurrence rates of preoperative single fraction partial breast radiation in early stage breast cancer. All analyses will be undertaken in the enrolled population who initiate treatment.

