13.1 Primary analysis, sample size, accrual and monitoring

The pCR and RCB status as assessed at surgery (defined in Section 2) will be tabulated, and the number and percentage of patients who achieve RCB 0/pCR or RCB 1 will be reported with two-sided 90% CIs. The primary endpoint will be rate of RCB 0 or 1.

Simon's two-stage design (Simon, 1989) will be used. The null hypothesis that the true response rate is 0.1 will be tested against a one-sided alternative. In the first stage, 16 patients will be accrued. If there are 1 or fewer responses in these 16 patients, a study team will be convened to determine if the study should proceed. Otherwise, 24 additional patients will be accrued for a total of 40. The null hypothesis will be rejected if 7 or more responses are observed in 40 patients. This design yields a type I error rate of 0.089 and power of 86.9% when the true response rate is 0.25.

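### Does permitting omission of sentinel biopsy at age 70 and over leave the RCB 0/I primary endpoint undefined?

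*Combined protocol and SAP*

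**What the plan says.** The primary endpoint is binary. Section 13.1 states: "The primary endpoint will be rate of RCB 0 or 1". Section 9.1 describes RCB as a published continuous index that "combines pathologic measurements of the primary tumor (size and cellularity) and nodal metastases (number and size", and section 3.3 likewise describes a system "which evaluates tumor size, nodal involvement and cellularity".

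Section 6.5 makes sentinel node assessment the default but adds that "omission of sentinel biopsy is permitted in patients age 70 and over with no clinical evidence of nodal involvement". Eligibility starts at age 50 with no upper limit, and every patient meets "4.1.5 Clinically node negative". Patients to whom the permission applies can therefore enroll.

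Section 6.6, directly after the permission, says that pathologic assessment includes RCB analysis and makes no exception. Section 9.1 repeats this and assigns the task to staff pathologists. On the population, section 13 states: "All analyses will be undertaken in the enrolled population who initiate treatment". Section 6.8 rules out replacing a withdrawn patient once radiation has begun. In section 13.1 the tabulation covers status at surgery, and "the number and percentage of patients who achieve RCB 0/pCR or RCB 1 will be reported". The same section sets the design: 16 patients first, with a study team convened at 1 or fewer responses; 40 in total; the null rate of 0.1 rejected at 7 or more responses.

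**The concern.** One input to the index can be absent by permission of the protocol, and sections 2.1, 6.6, 9.1 and 13.1 do not say what to do then. Sections 13 and 13.1 fix the denominator at 40 but not the class. Two handlings can be imagined:

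- **(a)** A patient without examined nodes has no complete RCB, so she has not achieved RCB 0/I and counts as a non-responder.
- **(b)** Her class comes from the breast component, with the nodal term at zero.

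With the same 40 patients, the two can fall on opposite sides of the limit of 7, and they can also move the look at 16. The trial is single-arm, so investigators can see responses as they accrue. A rule chosen once the counts are known could then decide the result. Section 3.3 adds to the worry by saying that the "requirement for multiple consecutive weeks of adjuvant radiation treatment puts older women" at a disadvantage, which suggests that older patients are part of the intended audience.

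**Working it through.** **Inputs.** From section 13.1: first stage 16, continue at 2 or more responses, total 40, reject at 7 or more, null rate 0.10, alternative 0.25. Two quantities are not in the documents and are assumed: *s*, the share of patients without sentinel biopsy (5 to 30%, or 2 to 12 of 40), taken as independent of response; and *q*, the share of apparent responders in that group whom nodal pathology would move out of RCB 0/I (5 to 20%).

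**Step 1: reproduce the plan's figures.** With the first-stage limit taken as binding,

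R(p) = Σ (x = 2 to 16) P(X₁ = x) · P(X₂ ≥ 7 − x), where X₁ ~ Bin(16, p) and X₂ ~ Bin(24, p).

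R(0.10) = 0.0890 and R(0.25) = 0.8690. Both match the stated 0.089 and 86.9%.

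**Step 2: handling (b), breast component.** Every patient has a class, and the response probability is the rate of the endpoint as scored. R(0.10) and R(0.25) are unchanged for any *s*.

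**Step 3: handling (a), non-responder.** The response probability becomes 0.25(1 − s). Responders under (a) are a subset of those under (b), so the difference in R is the probability of opposite decisions.

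| s | 0.25(1 − s) | Power under (a) | Opposite decisions | P(≤1 of 16) |
|---|---|---|---|---|
| 0 | 0.2500 | 86.9% | – | 6.3% |
| 5% | 0.2375 | 83.2% | 3.7% | 7.8% |
| 10% | 0.2250 | 78.6% | 8.3% | 9.6% |
| 20% | 0.2000 | 67.0% | 19.9% | 14.1% |
| 30% | 0.1750 | 52.3% | 34.6% | 20.2% |

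The first-stage limit only convenes a study team. On the final count alone, the disagreement at 0.25 is 3.4, 7.6, 19.0 and 33.9%. At the null rate, R(0.10) − R(0.10(1 − s)) is 1.7, 3.2, 5.6 and 7.1%.

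**Step 4: cost of (b) against a full breast-plus-node RCB.** If the full-RCB rate is 0.10, the scored rate is 0.10[(1 − s) + s/(1 − q)]. For s = 20% and q = 20% this is 0.10(0.80 + 0.25) = 0.105, and R(0.105) = 0.108. Over q = 5 to 20%, type I error is 0.091–0.098 at s = 10%, 0.093–0.108 at s = 20% and 0.095–0.119 at s = 30%.

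**Step 5: which handling does the text support?** Handling (a) needs a resected patient with no RCB class. Sections 6.6 and 9.1 call for RCB analysis as part of the pathologic work-up and carve out no group, although 6.6 comes straight after the permission. The nodal input in 9.1 is the number and size of metastases; a clinically node-negative patient with none found has nothing to enter. The only support for (a) is the verb in the reporting sentence of 13.1, which is ordinary language for a response count. Handling (b) fits all the sections together.

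**The case for a change.** The strongest case for a change is that the natural reading is still an inference. The protocol could have stated it in one sentence, the endpoint is primary, and even at 10% omission about one trial in twelve (8.3%) would change its conclusion with the handling. Nor can one lean on the published index or the institutional guidelines for the missing rule: their content is not in the documents. Handling (b) also has a cost of its own, since an occult positive node would go unseen and type I error against full RCB could pass 0.089.

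Part of this stands. The rule is not written down, and for some patients the endpoint would in effect be breast-only. The force of the argument weakens on three points. The disagreement figures need handling (a), which the text barely supports. They also need an omission rate that the documents do not give: the remark about older women in section 3.3 concerns missed adjuvant radiation, not this trial's age mix or how often sentinel biopsy is omitted. Finally, section 9.1 has staff pathologists assess RCB and section 13.1 refers to status assessed at surgery. Nothing suggests that classes are left open until tabulation, so the room for a choice after the counts are known is smaller than it first seems.

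**Conclusion.** The plan omits a detail; it does not contain a rule that gives a wrong result. Read together, sections 6.6, 9.1, 13 and 13.1 lead an analyst to score every resected patient from the available pathology and keep her in the 16 and the 40. Under that reading power does not fall, and 0.089 and 86.9% are right for the endpoint as scored.

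The power losses, down to 52.3% at 30% omission, illustrate a handling that is unlikely to be used, at assumed rates. The residual cost of the natural reading is a type I error of 0.091 to 0.119 against a full breast-plus-node RCB. That range assumes 10 to 30% omission, independent of response, and 5 to 20% of apparent responders in that group reclassified; none of these figures is in the documents.

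Writing the reading down would not alter the sample size, the limits or the stated error rates. Reporting how many patients were scored without nodal pathology is ordinary practice, and readers can then see whether the limits of 2 in 16 and 7 in 40 are met or missed however those patients are counted. No change to the plan is needed.
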